A patient will be considered a responder in Part A if he or she did not receive a blood transfusion from Week 5 through Week 26 (EOT) and did not receive treatment for CAgD beyond what is permitted per protocol. Additionally, the patient's Hgb level must meet either of the following criteria:

- Hgb level is ≥ 12 g/dL at the treatment assessment endpoint (defined as mean value from Weeks 23, 25, and 26), *or*
- Hgb increased ≥ 2 g/dL from baseline (defined as the last Hgb value before administration of the first dose of study drug) at treatment assessment endpoint

Note: Any patient withdrawing from the study after Week 5 and prior to the Week 23 visit will be considered a non-responder.

A list of excluded concomitant medications, as well as allowed concomitant medications with restrictions, is provided in [Section 6.2.6](#). Beyond the permitted concomitant medications, study drug, and transfusions, patients may receive no other therapies for the treatment of CAgD while enrolled in this study; patients requiring other treatment for their CAgD in Part A will be withdrawn from the study and counted as non-responders. These patients will not be eligible to participate in Part B.

Part B

Following completion of dosing in the 6-month treatment period, patients will continue to receive BIVV009 dosing during Part B, the long-term safety and durability of response extension phase. Part B will run for 2 years following last patient out (LPO) under Part A. Patients requiring treatment with permitted concomitant medications and/or transfusions will not be discontinued from the study. Patients in Part B will be transfused per the Transfusion Criteria in [Table 1](#). Patients who receive a transfusion during Part B will not be withdrawn from the study.

Patients will be dosed with BIVV009 every 2 weeks, as in Part A. Should patients deviate from their scheduled dosing, a repeat loading dose may be required. On-site visits will be completed ~ every 3 months (at a minimum) for collection of PK, PD and ADA samples during the 1st year of treatment in Part B, then every 6 months and for additional safety and efficacy measures.

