5.3 REMOVAL OF PATIENTS FROM STUDY PARTICIPATION, AND STUDY SUSPENSION AND STOPPING RULES

Patients will be informed that they are free to withdraw from the study at any time and for any reason. Patients should inform the site of withdrawal in writing. The Investigator (or designee) may remove a patient from the study if, in the Investigator's (or designee's) opinion, it is not in the best interest of the patient to continue the study. Patients may be withdrawn due to the following:

- Change in compliance with inclusion/exclusion criteria that is clinically relevant and affects patient safety.
- Occurrence of AEs that, in the opinion of the Investigator, may jeopardize patient safety or data integrity. This includes clinically significant hematologic breakthrough events attributable to the development of ADA and/or the development of positive SLE auto-antibody titers.
- Occurrence of pregnancy in patient while receiving study drug.
- Intake of non-permitted concomitant medication that might affect patient safety or study assessments/objectives.
- Clinical signs of SLE or any other immune complex disease.

The Investigator will immediately notify the Sponsor's Study Monitor of all patients who withdraw from treatment. In case of withdrawal, all ET assessments should be performed as applicable ([Section 6.1.4](#)). The date the patient is withdrawn from the study and the reason for withdrawal will be recorded on the patient's electronic Case Report Form (eCRF). All withdrawn patients will be followed until resolution of all their AEs or until the unresolved AEs are judged by the Investigator (or designee) to have stabilized. Patients who withdraw from study early (prior to Week 5) may be replaced at the discretion of the Sponsor. Patients who withdraw from study after Week 5 and prior to Week 23 will not be eligible to participate in Part B.

The entire study may be discontinued at the discretion of the Sponsor based on the occurrence of the following:

- Adverse events unknown to date or increased frequency and/or severity, and/or duration of known AEs
- Results of the interim analysis ([Section 7.9](#)) demonstrating absence of clinically significant increases in Hgb
- Medical or ethical reasons affecting the continued performance of the study
- Difficulties in the recruitment of patients
- Cancellation of or change in drug development program per the discretion of the Sponsor

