5.1.3. Estimands

Following [International Conference on Harmonisation \(2014\)](#) and [National Research Council \(2010\)](#), the following estimands are considered for efficacy endpoints to provide clarity of what to be estimated and its connection to the trial objectives. [Akacha, et. al. \(2017\)](#) proposed a framework for defining an estimand using three attributes:

- The population of interest;
- The variable to be used for the clinical question, which consists of measurements at a specific timepoint. It could be a composite endpoint that incorporates post-randomization events.
- The measure of intervention effect, which accounts for potential effects of post-randomization events.

A composite estimand will be used for the primary endpoint and a hypothetical estimand will be used for lab parameter defined secondary endpoints. Alternative estimands are also proposed to either assist the interpretation of primary estimand or used for exploratory endpoints.

Composite Estimand

- Population: FAS
- Variable: A composite endpoint: endpoint response criteria, and remain in the study through at least Week 23 visit (i.e., patients who discontinued the study participation prior to Week 23, including those who discontinued prior to Week 5, are considered non-responder)
- Measure of Intervention Effect: Proportion of subjects who respond according to the variable definition

Hypothetical Estimand

- Population: FAS

- Variable: Change from baseline at treatment assessment timepoint (Weeks 23, 25, and 26), where any post-baseline value after transfusion and prohibited medication (from Week 5 to Week 26) is considered missing
- Measure of Intervention Effect: Mean change from baseline, had transfusion and prohibited medications not been available

De-Facto Estimand

- Population: FAS
- Variable: Change from baseline at treatment assessment timepoint (Weeks 23, 25, and 26)
- Measure of Intervention Effect: Mean change from baseline, irrespective of transfusion or prohibited medications

Observed Estimand

- Population: a subset of FAS, subjects who remain in the study through at least the visit of interest (e.g., Week 23) and have at least 1 evaluable parameter or score at target visits.
- Variable: Change from baseline at the visit of interest, or response at the visit of interest
- Measure of Intervention Effect: Mean change from baseline or proportion of subjects who respond, irrespective of transfusion or prohibited medications

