5.1.4. Handling of Missing Data

Best efforts will be utilized to minimize missing values. If a subject discontinues study treatment early, the subject will be asked to complete study assessments at EOT/safety follow up visit.

For the primary endpoint, which is a composite endpoint of avoidance of transfusion and improvement of Hgb at the treatment assessment timepoint (i.e., Weeks 23, 25, and 26), missing either component results in a missing value for the endpoint. The improvement of Hgb at the treatment assessment timepoint is missing only if no Hgb value is available for all 3 visits (Weeks 23, 25, and 26). Since pre-treatment Hgb is a key requirement to enroll in the study, it is reasonable to assume that all enrolled subjects have at least 1 Hgb prior to the study treatment, which constitutes the baseline Hgb value (see [Section 5.1.1](#)).

For the primary analysis of the primary endpoint, the composite estimand is utilized. Hence, a missing value will be considered a non-response. Other sensitivity analyses specified in [Section 7.2.2](#) will be performed to evaluate the impact of missing values, when appropriate. However, other responder-type endpoints will be analyzed using observed data only.

For the analysis of continuous variables (e.g., secondary endpoints), summary statistics will be computed based on observed data. To analyze lab parameter (e.g., Hgb, bilirubin, LDH) changes attributable to the study treatment (hypothetical estimand), values post any transfusion (after Week 5) or protocol prohibited CAD treatment (defined in [Section 5.1.1](#), after Week 5) will be

censored. The mean change from baseline will be estimated using Mixed Model for Repeated Measures (MMRM) along with its 95% CIs. Multiple Imputation will also be used to estimate the mean change from baseline at treatment assessment timepoint and its associated 95% CI. All these analyses assume missing at random (MAR).

Although the assumption of MAR cannot be verified, the mechanism of missing data due to transfusion or prohibited medication use described below supports such an assumption.

- The protocol (Table 1) specifies the transfusion criteria, which is comprised of the Hgb level.

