- Despite the use of prohibited medications not being allowed by the protocol, the potential need for the use of rituximab and/or combination therapy would be mostly due to the lack of response or hematologic breakthrough, which is specified in the protocol by changes in the level of Hgb and other hemolytic markers.

Therefore, the missing data due to the occurrence of transfusion and prohibited medication use is expected to be triggered by low levels of Hgb and other hemolytic markers, which are observable. Because of this mechanism, it is reasonable to assume that the probability of missing data due to transfusion or prohibited medication use is a function of the observed Hgb or other hemolytic marker levels; hence, supports the assumption for MAR.

Additional sensitivity analyses, specified in the particular endpoints, may be carried out to examine the validity of the assumption of MAR. Multiple imputation based on models compatible with Missing Not At Random (MNAR) missing mechanism may be used, where missing values at treatment assessment visit will be imputed by using Neighboring-Case Missing Value (NCMV) restriction. Certain adjustment may be needed for NCMV approach due to the small sample size, where there may be lack of neighboring cases.

Supportive analysis based on de-facto estimand will also be performed using MMRM to estimate the mean change from baseline along with its 95% CIs.

For a QOL endpoint, in the event of missing data, the total score will be estimated according to the provision for missing domains in the calculation algorithm of the score. For example, if a subject has missing data in questionnaires at a visit, the prorated FACIT-F score will be calculated, if more than 50% of items (a minimum of 7 out of 13 items) are available. Otherwise, the score is missing.

For exploratory endpoints, observed estimands will be used unless specified otherwise.

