7.3.5. Mean Change from Baseline in Hgb at the Treatment Assessment Timepoint

The change from baseline in Hgb at the treatment assessment timepoint will be analyzed for the FAS. The primary analysis will be performed according to Hypothetical Estimand (defined in

[Section 5.1.3](#)), while a sensitivity analysis will be done via De-facto Estimand ([Section 5.1.3](#)). Additional details are found in [Table 7](#).

Table 7: Estimands for Change from Baseline in Hgb

	Hypothetical Estimand	De-facto Estimand
Population	FAS	FAS
Variable	Change from baseline at treatment assessment time point, where any value after transfusion and prohibited medication is considered missing	Change from baseline at treatment assessment time point
Treatment effect	Mean change from baseline, if transfusion or prohibited medications had not been available	Mean change from baseline, irrespective of transfusion or prohibited medication use

For either estimand, the mean change from baseline in Hgb at treatment assessment timepoint, along with its 95% CI, will be estimated by the MMRM model ([Section 5.1.4.1](#)).

Additional sensitivity analyses for hypothetical estimand, similar to those specified for bilirubin, will be performed for the change from baseline in Hgb at treatment assessment timepoint.

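### The de-facto estimand covers prohibited medication, but the protocol withdraws those patients, so most of their Week 23, 25 and 26 values are never collected

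*Protocol*

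**What the plan says.** Part A SAP Section 5.1.3 defines the de-facto estimand in the full analysis set as "Mean change from baseline, irrespective of transfusion or prohibited medications", at Weeks 23, 25 and 26. Tables 4 to 7 repeat it for bilirubin, FACIT-Fatigue, LDH and Hgb. Section 5.1.4 names the estimator: "Supportive analysis based on de-facto estimand will also be performed using MMRM to estimate the mean change from baseline along with its 95% CIs". Section 5.1.4.1 gives the model terms as baseline value and visit.

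The protocol treats the two events differently. Under Section 4.1, transfused patients stay in the study. For other therapy the same section says "patients requiring other treatment for their CAgD in Part A will be withdrawn from the study and counted as non-responders". Section 5.3 is softer. It introduces its list with "Patients may be withdrawn due to the following", and the list includes "Intake of non-permitted concomitant medication that might affect patient safety or study assessments/objectives".

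For early discontinuation, SAP Section 5.1.4 says "the subject will be asked to complete study assessments at EOT/safety follow up visit". Protocol Section 6.1.7 places that visit 9 weeks after the last dose and includes hematology, chemistry and FACIT-Fatigue. SAP Section 5.1.1 lets the value stand in for a missing visit if it falls in that visit's window in Table 1.

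**The concern.** An estimand that holds whatever happens after an event needs data from after the event. The transfusion half has them, because those patients remain under observation. The prohibited-medication half mostly does not if Section 4.1 is applied as written.

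The SAP itself (Section 5.1.4) expects prohibited therapy to be used mainly for lack of response or hematologic breakthrough. These are the patients for whom a sensitivity analysis is most useful. If their endpoint values are largely predicted by the model in both the hypothetical and the de-facto analysis, agreement between the two may be read as robustness to rescue by other therapy when it has hardly been tested. No other planned analysis would show this: the multiple-imputation models, including the one with neighboring-case restrictions, are specified for the hypothetical estimand only (Section 7.3.1), and the table list in Section 12 has no imputation output for the de-facto estimand.

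**Working it through.** **1. The plan's own figure.** The documents give no figure for the de-facto mean change. The nearest is the power for the primary endpoint (Protocol Section 7.10). The exact binomial with N = 20, success at 11 or more and a true rate of 66% gives 0.897 against the stated 90%. The Clopper-Pearson lower limit is 0.315 for 11/20 and 0.272 for 10/20. Nothing below changes these.

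**2. Where the follow-up visit lands.** Inputs: dosing days (Protocol Section 4.1), 9 weeks = 63 days (Section 6.1.7), and the study-day convention and windows (SAP Section 5.1.1, Table 1). Protocol Day 0 is Study Day 1, so

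visit study day = last-dose day + 63 + 1.

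| Last dose (protocol day) | Visit, study day | Window |
|---|---|---|
| 0, 7 | 64, 71 | Week 9 |
| 21 | 85 | Week 11 |
| 35 | 99 | Week 13 |
| 49 | 113 | Week 15 |
| 63 | 127 | Week 17 |
| 77 | 141 | Week 19 |
| 91 | 155 | Week 21 |
| 105 | 169 | **Week 23** |
| 119 | 183 | **Week 26** |
| 133, 147, 161 | 197, 211, 225 | none (last window ends on Day 189) |

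Of the 13 last-dose days before Day 175, 2 put the value in an endpoint window, 8 in an earlier visit and 3 nowhere (2 + 8 + 3 = 13). The visit window of ±2 days changes little: a visit 1 or 2 days late moves Day 91 into Week 23 and Day 105 into Week 25. A patient last dosed on Day 161 also has a predose Week 23 value from that visit (Protocol Section 6.1.3).

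**3. What the model does.** For last doses on Days 105 and 119, one endpoint visit is observed and the other two are predicted. For Day 91 or earlier, the off-drug value informs Weeks 23–26 only through the within-patient covariance. For Days 133 and 147 the patient has neither an off-drug value nor an endpoint value. In each case the missing endpoint visits are predicted under missing at random, from the patient's own data and from those who stayed. No model term marks the change of therapy.

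**4. Possible size.** If k of 20 patients are withdrawn, the error in the mean is approximately

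k/20 × (value implied by the model − true value).

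Taking an implied change of +1.0 g/dL (assumed):
- k = 1: 1/20 × (1.0 − (−1.5)) = +0.125; 0 if the true change is +1; 1/20 × (1.0 − 3) = −0.10.
- k = 3: +0.375, 0 and −0.30.

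A simulation puts a fitted model in place of the assumed implied value. Its assumptions are: 20 patients; on-drug mean Hgb change rising to about +2.6 g/dL; between-patient SD 1.2; visit SD 0.8 with serial correlation 0.5; the two lowest early responders withdrawn, with last doses on Days 77 and 119; 150 trials per case. The fit used visit means with a random intercept and AR(1) errors, not the SAP's heterogeneous Toeplitz structure, and no baseline covariate.

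| True change after withdrawal (g/dL) | Error, follow-up value not used | Error, follow-up value used |
|---|---|---|
| −1 | +0.19 | +0.09 |
| 0 | +0.09 | +0.04 |
| +1 | −0.01 | 0.00 |
| +2 | −0.12 | −0.06 |
| +3 | −0.21 | −0.10 |

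Monte Carlo standard errors are 0.003 to 0.005. The sign changes near +1 g/dL, and using the follow-up value roughly halves the error.

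**The case against.** The strongest defense is that the prohibited-medication clause is not empty. Section 5.3 makes withdrawal for non-permitted medication discretionary. The SAP asks about such medication at post-baseline visits (Section 5.1.1), lists it as an important deviation (Section 6.3), and keeps it separate from remaining in the study in the composite estimand (Table 3). It evidently expects to observe some users. The follow-up value also enters some visit window for 10 of the 13 last-dose days, and the model conditions on each patient's own poor earlier values. Finally, this is a sensitivity analysis of secondary endpoints, for which SAP Section 7.1.1 plans no formal test.

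Most of this stands, and it rules out two stronger readings. A reader might infer that the de-facto analysis is the hypothetical one under another name, with these patients filled in as if still on drug. The documents do not support that: the hypothetical analysis discards values after prohibited treatment, while the de-facto analysis keeps any that exist, including the follow-up value. A reader might also infer that the mean change is overstated. That is not shown, because the stated target includes whatever the other therapy achieves. The relapse on washout described in Protocol Section 2.2.2 concerns stopping BIVV009, not moving to another treatment.

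The defense does not supply planned data. Discretion in Section 5.3 conflicts with Section 4.1 and schedules no assessments after withdrawal, and one off-drug value assigned to an earlier visit does not observe Weeks 23 to 26.

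**Conclusion.** The point holds as a mismatch between estimand, data collection and estimator. For patients who need other treatment for their disease in Part A, the de-facto analysis relies largely on missing-at-random prediction and does not deliver a mean change irrespective of prohibited medication. For transfusion it does, because those patients stay.

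The error can go either way: upward if withdrawn patients relapse, downward if the other therapy works. Its size cannot be derived from the documents, which give neither the number withdrawn nor their later values; the figures above only illustrate the scale. The window mapping assumes that visits occur on schedule and that Section 4.1 is applied as written; if patients are kept under Section 5.3, the gap shrinks. The consequence is confined to a sensitivity analysis of four secondary endpoints. The primary endpoint counts these patients as non-responders and is unaffected.

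**What to change.** 1. In SAP Section 5.1.3 and Tables 4 to 7, restate the de-facto estimand as irrespective of transfusion, which is the part that is observed.
2. Report how many patients have no Week 23, 25 or 26 data after starting other treatment.
3. Add a supplementary multiple-imputation analysis of the de-facto estimand under missing not at random, over a range of delta shifts that includes return to baseline, keeping any observed follow-up values. A range is better than return to baseline alone because the direction is uncertain.
4. If any Part A follow-up remains, collect the Week 23, 25 and 26 assessments after withdrawal instead. The wording about prohibited medication could then stay.
5. Reconcile the mandatory withdrawal in Protocol Section 4.1 with the discretionary wording in Section 5.3. At the same time, correct the Section 5.3 cross-reference for early-termination assessments: it points to Section 6.1.4 (the Week 26 visit), while the early-termination visit is in Section 6.1.7.

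Cost: SAP wording, one extra imputation run per endpoint, up to three visits for each withdrawn patient if item 4 applies, and possibly a less favorable sensitivity result.

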4.2 DISCUSSION OF STUDY DESIGN

The route of administration, dose, and dosing interval for BIVV009 planned for use in this study are based on the initial Phase 1a/1b clinical experience (BIVV009-01) and corresponding non-clinical data for safety, PK, and PD observations. BIVV009 has thus far been administered to healthy human volunteers and patients with complement-mediated disease entities including CAgD, bullous pemphigoid, warm autoimmune hemolytic anemia, and AMR.

Under the current protocol, enrolled patients will receive fixed doses of BIVV009 via IV infusion of either 6.5 grams (if <75 kg) or 7.5 grams (if \geq 75 kg), based on their baseline body weight.

The repeated dose regimen is predicted to provide continuous C1s inhibition throughout the dosing interval, with an adequate safety margin based on comparative drug exposures in NHPs ([Section 2.2.1](#)) and in healthy volunteers given a single dose of 100 mg/kg in Phase 1a ([Section 2.2.2](#)).

Safety, tolerability, PK, and PD and immunogenicity assessments will be evaluated at the time points indicated in the study schedule of events ([Table 3](#)). In patients having consented to the use of their blood samples for future research, ADA may be tested using available predose PD back-up samples.

4.3 STUDY ENDPOINTS

4.3.1 Primary endpoint (Part A)

The primary efficacy endpoint is the responder rate as defined in [Table 2](#).

4.3.2 Secondary efficacy endpoints (Part A)

- Mean change from baseline in bilirubin (excluding patients with Gilbert's Syndrome) at the treatment assessment endpoint (defined as the mean value of Weeks 23, 25, and 26)
- Mean change from baseline in QOL, as assessed by the change in Functional Assessment of Chronic Illness Therapy (FACIT)-Fatigue scale ([Section 10.3](#), Appendix C) scores at the treatment assessment endpoint
- Mean change from baseline in lactate dehydrogenase (LDH) at the treatment assessment endpoint

- Number of transfusions and number of units after the first 5 weeks of study drug administration
- Mean change from baseline in Hgb at the treatment assessment endpoint

